10.1.3 Day 1 and Day 8 (Telephone Contact)

The following procedures will be performed during the Day 1 (+ 1 day) and Day 8 (- 1 day/+ 1 days) phone contact:

- Ask the subjects to use their MA to support their recall in providing information during the scheduled phone interview;
- Ask the subjects about any difficulties in completing the MA, any change in health, any visits to health care facilities and/or medical practitioners, and any use of concomitant medications. Record the information in the source documents;
- For any unsolicited AEs and/or solicited local and systemic reactions of greater than Grade 2 (moderate), the Investigator should be informed within 48 hours of the time the clinical site is made aware of the event. The Investigator may request that the subject return to the clinic for evaluation;
- Advise subjects to immediately contact the Investigator (or his/her designee) in the event of any AE that requires medical attention. Subjects will be provided with a phone contact number and be instructed to call if any suspected reaction to the vaccination is felt to be significant or of concern;
- Remind the subjects how to measure and record any solicited local and systemic reactions. Subjects should also be reminded to record any changes in health, including changes in AEs and changes in medications and to record this information on the appropriate MA pages. Remind the subjects to record PRN intake;
- Remind subjects of their next appointment (date and time) for the clinical visit and/or the next phone contact. Subjects will also be reminded to bring back the MA for their Day 21 visit;

In the event that a subject cannot be reached via phone, he/she may be contacted by text message or via email (if these contacts are available). However, the phone should be the initial and preferred means of communication.

10.1.4 Day 21 (Visit 2)

The following procedures will be performed during the Day 21 (-2/+3 days) visit:

- Collect and review the MA content with the subject to ensure appropriate completion. Corrections must be made by the subject him/herself and all corrections must be initialed and dated. In the event that a subject is not able to make the correction him/herself, the site personnel will be authorized to enter a clarification in the comments section of the MA with a proper explanation. The original MA will be kept in subject's chart;
- Record any changes in the subject's health, any complaints of lymphadenopathy, any visits to health care facilities and/or medical practitioners, and any concomitant medication use

(including any vaccines received) since the Day 8 phone contact and confirm that the subject has continued to comply with the protocol requirements (e.g. no use of prohibited concomitant medications, use of an adequate contraceptive method);

- Perform a lymphadenopathy examination if the subject complains of arm or shoulder pain of the vaccinated arm or neck pain at the time of the visit (a directed exam for lymph node swelling of the neck and axilla). In addition, a history/symptom-directed physical examination can also be performed, based on the Investigator's opinion. These examinations should be performed by the Investigator;
- Collect a blood sample for HI assessment and prepare and store the sample until shipment to the analytical laboratory;
- Collect a urine sample for all female subjects and a perform urine dipstick pregnancy test.

Any subject who withdraws consent from the study prior to completion of the Day 21 visit will be asked to return their MA to the clinic site and to provide an update on their health status and concomitant medication usage (if the subject agrees).

10.2 Immunogenicity

10.2.1 Evaluations

Immunogenicity will be evaluated by the humoral immune response (HI assay) induced in subjects on Day 0 and Day 21.

10.2.2 Immunogenicity Endpoints

10.2.2.1 Primary Immunogenicity Endpoints

- GMTs of the three vaccine lots (21 days after vaccination) for all four vaccine strains:
 - Lot-to-lot consistency is based on adjusted GMT ratios for pairwise comparisons of the lots (lot 1/lot 2, lot 1/lot 3, and lot 2/lot 3). Lot-to-lot consistency will be demonstrated if the two-sided 95 % CI limit falls between 0.67 and 1.5 for all four strains.

10.2.2.2 Secondary Immunogenicity Endpoints

- HI antibody response induced by the Quadrivalent VLP Influenza Vaccine (pooled data from the three lots) against the homologous influenza strains on Days 0 and 21; HI antibody titers will be analyzed as follows:
 - SC rate: the proportion of subjects with either a \geq 4-fold increase in reciprocal HI titers between Day 0 and Day 21 or a rise of undetectable HI titer (i.e. < 10) pre-vaccination (Day 0) to an HI titer of ≥ 40 on Day 21;
 - SP rate: the proportion of subjects attaining a reciprocal HI titer of ≥ 40 on Day 21 (the percentage of vaccine recipients with a serum HI titer of at least 1:40 following vaccination);
 - GMFR: geometric mean of the ratio of GMTs (Day 21/Day 0).

Confidential Information

The immunogenicity endpoints for all four homologous influenza antigens will be evaluated according to the CBER criteria for SC rate and SP rate.

10.3 Safety

10.3.1 Evaluations

Safety and tolerability will be evaluated by solicited local and systemic reactions (immediate complaints within 15 minutes post-vaccination and reactions up to seven days post-vaccination), and unsolicited SAEs, NOCDs, and AEs up to 21 days post-vaccination.

10.3.1.1 Solicited Local and Systemic Reactions

Subjects will be monitored for both solicited local reactions (erythema, swelling and pain at the injection site) and solicited systemic reactions (fever, headache, fatigue, muscle aches, joint aches, chills, a feeling of general discomfort, swelling in the axilla, and swelling in the neck) from the time of vaccination through Day 7. While the subjects remain in the clinic following vaccine administration, staff will monitor them for local and systemic reactions. After release from the clinic facility, from Day 0 to Day 7 (preferably in the evening), subjects will measure and record their local and systemic reactions in their MA.

The intensity of the solicited local and systemic reactions will be graded as: mild (1), moderate (2), severe (3) or potentially life threatening (4), as defined below in [Table 5](#). Their causal relationship with the study vaccine will be assessed by the Investigator (definitely not related, probably not related, possibly related, probably related, or definitely related); see Section [13.1.9](#) for a definition of these causal relationships.

Table 5 Severity Grades for Solicited Local and Systemic Reactions

Symptoms	Severity				
	None	Grade 1 (Mild)	Grade 2 (Moderate)	Grade 3 (Severe)	Grade 4 (Potentially life-threatening)
Injection Site Reactions (Local Reactions)					
Erythema (redness)	< 25 mm	25 - 50 mm	51 - 100 mm	> 100 mm	Necrosis or exfoliative dermatitis
Swelling	< 25 mm	25 - 50 mm and does not interfere with activity	51 - 100 mm or interferes with activity	> 100 mm or prevents daily activity	Necrosis
Pain	None	Does not interfere with activity	Repeated use of non-narcotic pain reliever for more than 24 hours or interferes with activity	Any use of narcotic pain reliever or prevents daily activity	Results in a visit to emergency room (ER) or hospitalization

Symptoms	Severity				
	None	Grade 1 (Mild)	Grade 2 (Moderate)	Grade 3 (Severe)	Grade 4 (Potentially life-threatening)
Solicited Systemic Reactions					
Fever (°C)	< 38.0 °C	38.0 - 38.4 °C	38.5 - 38.9 °C	39.0 - 40.0 °C	> 40.0 °C
Headache	None	No interference with activity	Repeated use of non-narcotic pain reliever for more than 24 hours or some interference with activity	Significant; any use of narcotic pain reliever or prevents daily activity	Results in a visit to emergency room (ER) or hospitalization
Fatigue	None	No interference with activity	Some interference with activity	Significant; prevents daily activity	Results in a visit to emergency room (ER) or hospitalization
Muscle aches	None	No interference with activity	Some interference with activity	Significant; prevents daily activity	Results in a visit to emergency room (ER) or hospitalization
Joint aches, chills, feeling of general discomfort or uneasiness (malaise), swelling in the axilla, swelling in the neck	None	No interference with activity	Some interference with activity not requiring medical intervention	Prevents daily activity and requires medical intervention	Results in a visit to emergency room (ER) or hospitalization

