- How to measure any solicited local reactions, including erythema (redness) and swelling diameter at the injection site using the measurement template supplied for this purpose; subjects will also be requested to evaluate pain at the injection site. Local reactions will be assessed every day from Day 0 to Day 7 (preferably in the evening); the results will be recorded in the MA. The severity of solicited local reactions will be graded according to the Food and Drug Administration (FDA) Guidance for Industry: Toxicity Grading Scale for Healthy Adult and Adolescent Volunteers Enrolled in Preventive Vaccine Clinical Trials ([FDA, 2007](#)), as presented in [Table 5](#);
- How to grade, on a daily basis from the Day 0 to Day 7 (preferably in the evening), each of the solicited systemic reactions and their severity (as per the same guidance used for solicited local reactions; see [Table 5](#)) ([FDA, 2007](#)) and to record the worst grade of the day for each of these solicited systemic reaction in the MA. The instructions will include how to examine and grade swelling in the neck and axilla and to record any unusual feeling and/or swelling in the MA;
- To use their MA to support their recall in providing information during the scheduled phone interview conducted on Days 1 and 8 and to bring their MA with them to the Day 21 clinic visit. The staff will review the MA entries and grade these entries with the subject;
- To record new use of medication in their MA, in addition to each intake of PRN drugs;
- Subjects will be advised that they will be asked about the occurrence of any symptoms or events requiring medical attention and the use of any concomitant medication during the 21-day post-vaccination period;
- Subjects will be instructed to contact the clinical site for any unsolicited AEs and/or solicited local and systemic reactions of greater than Grade 2 (moderate). Based on their condition, the Investigator may request that the subject return to the clinic for evaluation;
- Subjects will be advised on emergency contact information and instructions for contacting study personnel. Subjects will be advised to immediately contact the Investigator (or his/her designee), in the event of an SAE or a medical emergency. Subjects will be provided with a phone contact number and be instructed to call if any suspected reaction to the vaccination is felt to be significant or of concern;

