19 APPENDICES

19.1 Appendix 1 – Sample Memory Aid Diary (Day 0 to Day 21)

MEMORY AID (DAY 0 to DAY 21)	
Study Name	A Randomized, Observer-blind, Multicenter, Phase 3 Study to Evaluate the Lot Consistency, Immunogenicity, and Safety of a Plant-Derived Quadrivalent VLP Influenza Vaccine in Healthy Adults 18-49 Years of Age
Protocol Number	CP-PRO-QVLP-011
Sponsor	Medicago R&D Inc. [name]
Clinical site Address	
Principal Investigator Name	
Clinical Research Coordinator	
24-hour Emergency Number	

SAMPLE ONLY - DO NOT USE

INSTRUCTIONS

SYMPTOMS (pages 4 to 6):

- Complete the table referring to the following periods:
 - For the 1st column: the period between the vaccination and the 15 minutes post-dose
 - For the 2nd column: to the period between the vaccination and the evening
 - For the remaining columns: the period since the previous evaluation of the symptoms
- If the symptom is not present, indicate 0.
- If the symptom is present, a grade should be indicated.
- Use the measuring tool given to you at the site to estimate the size of the red/swollen area around the injection site. Indicate the grades for the Redness and Swelling at injection site on the next page.
- Evaluate the grade of all other symptoms according to the definitions:
 - **0= No symptom**
 - **1= Mild: Does not interfere with activity**
 - **2= Moderate: Repeated use of non-narcotic pain reliever (e.g. Advil, Tylenol) >24 hours or interferes with activity**
 - **3= Severe: Any use of narcotic pain reliever (e.g. codeine, morphine) or prevents daily activity**
 - **4= Potentially life-threatening: Visit to Emergency room or hospitalization**
- List any other problems (not listed on pages 4 to 6) on page “side effects (symptoms)”.
- Symptoms listed on pages 4 to 6 which persist longer than 7 days after study vaccine administration should also be listed on page “side effects (symptoms)”.

SIDE EFFECTS (Symptoms) and MEDICATION:

- Use the space provided to record important information that you want to tell us about changes in your health. Note any health problems you experience, worsening of previous problems, or new medicines you take. Examples may include prescription drugs (including vaccines), over-the-counter drugs, herbal supplements and/or vitamins.
- It is especially important that you make a note of problems that required a visit to your doctor, a hospital stay, or a visit to emergency room.

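### The sample memory aid and ruler grade 8 of 12 solicited reactions by criteria that differ from Table 5, and no passage tells staff to re-grade those entries to Table 5

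*Protocol*

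**What the plan says.** **The prescribed scale.** Protocol 10.3.1.1 lists the four grades, ending "potentially life threatening (4), as defined below in" Table 5. Protocol 10.1.2.3 sends subject training to the same place: local reactions are graded as in Table 5, and systemic reactions "as per the same guidance used for solicited local reactions; see" Table 5.

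**What Table 5 contains.** Joint aches, chills, malaise, axillary swelling and neck swelling share one row. Grade 2 is "Some interference with activity not requiring medical intervention" and Grade 3 is "Prevents daily activity and requires medical intervention". Fatigue and muscle aches are graded on activity alone. Injection-site swelling reaches Grade 2 at "51 - 100 mm or interferes with activity", with a parallel activity route to Grade 3.

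**What the subject's tools contain.** Appendix 1 applies one generic key to every symptom other than redness and swelling. Its Grade 3 is "Any use of narcotic pain reliever (e.g. codeine, morphine) or prevents daily activity"; its Grade 2 pairs repeated non-narcotic analgesic use with interference. Appendix 2 grades redness and swelling by millimetres up to Grade 3. The diary is marked "SAMPLE ONLY - DO NOT USE".

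**Review.** Protocol 10.1.2.3 adds: "The staff will review the MA entries and grade these entries with the subject". The solicited pages carry a physician sign-off, and the diary is reviewed at Day 21 (Protocol 10.1.4, 10.3.4).

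**Use of the grades.** SAP 9.1.1 names Grades 1 to 4 without citing a scale. SAP 9.1.4 includes the proportion of subjects with a non-zero grade. SAP 9.1.6 and the table index plan summaries by maximum severity (14.3.1.3, 14.3.1.6) and of severe or potentially life-threatening related reactions (14.3.1.8).

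**The concern.** Intensity of solicited reactions is a named safety endpoint (Protocol 10.3.3). A severity table is interpretable only if each grade has one meaning. Here the subject may grade on one set of criteria while the protocol defines the grade on another. If staff carry some entries across unchanged and re-grade others, a count of severe chills, for example, combines two definitions.

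The same grades drive the instruction to contact the site, and to inform the investigator, for reactions above Grade 2 (Protocol 10.1.2.3, 10.1.3). The subject applies that instruction at home, with the diary key in hand, before any staff review.

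**Working it through.** The plan states no figure on this point, so the check is a comparison of definitions.

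**Step 1: criteria side by side.** Codes: I = interferes with activity; P = daily activity prevented; A = repeated non-narcotic analgesic for more than 24 hours; N = any narcotic analgesic; M = medical intervention required. Each entry is Grade 2 / Grade 3.

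| Reaction | Table 5 | Sample diary or ruler | Differs |
|---|---|---|---|
| Erythema | 51–100 mm / >100 mm | 51–100 mm / >100 mm | no |
| Injection-site swelling | 51–100 mm or I / >100 mm or P | 51–100 mm / >100 mm | yes (1) |
| Pain | A or I / N or P | A or I / N or P | no |
| Headache | A or I / N or P | A or I / N or P | no |
| Fever | °C bands | °C recorded, no grade | no |
| Fatigue, muscle aches | I / P | A or I / N or P | yes (2) |
| Joint aches, chills, malaise, axillary swelling, neck swelling | I and not M / P and M | A or I / N or P | yes (5) |

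Count: 1 + 2 + 5 = 8 of 12. Headache differs only in qualifying words, so it is not counted. At Grade 4, erythema and injection-site swelling are also worded differently: tissue loss with blister or ulcer on the ruler, against necrosis (for erythema, also exfoliative dermatitis) in Table 5.

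**Step 2: direction, below emergency-room level.** Combinations are unweighted. Self-taken pain relief and medical intervention are treated as separate items, which is an assumption.

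- *Five grouped reactions:* 3 activity levels × 3 analgesic levels × 2 intervention states = 18 combinations. Table 5 grades 12: 6 with no interference, 3 with I and not M, 3 with P and M. Of these, 7 agree, the diary is higher in 5 and lower in 0. The other 18 − 12 = 6 have no Table 5 grade: 3 with P and not M, 3 with I and M.
- *Fatigue and muscle aches:* 3 × 3 = 9 combinations each. In 6 the scales agree, and in 3 the diary is higher. Example: fatigue without interference but with A is diary Grade 2 and Table 5 Grade 1.
- *Injection-site swelling, tissue intact:* 4 size bands × 3 activity levels = 12 combinations. The ruler is lower in 5 and agrees in 12 − 5 = 7. Two of the 5 are under 25 mm, where Table 5's own size and activity columns overlap, so 5 − 2 = 3 are unambiguous. Example: 25–50 mm with interference is ruler Grade 1 and Table 5 Grade 2.

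**Step 3: effect on incidence.** Swelling under 25 mm that affects activity is Grade 0 on the ruler but can be read as Grade 2 or 3 in Table 5. It could therefore drop out of the non-zero-grade proportion in SAP 9.1.4.

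**Step 4: can staff recover the Table 5 grade?** Of the 12 solicited rows, one (oral temperature) records a raw value, and 12 − 1 = 11 record severity only as a grade. The solicited pages have no field for medical intervention or for activity interference with swelling. Elsewhere, the Day 1 and Day 8 calls and the Day 21 visit ask about health-care contacts, and the diary's medication page records drugs with the reason for use. For systemic reactions, this supports partial re-grading. For injection-site swelling, activity interference has no dedicated field.

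**The case against.** The strongest reply is that the protocol already settles the scale: 10.3.1.1 is unqualified, staff grade the entries with the subject, and no passage makes the subject's own grade the analysis grade. Much of this stands. A reader might infer that no severity rule exists at all; that goes too far, because Table 5 is the default. What remains is that the staff-grading sentence names no scale and no conversion.

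A reader might also infer that the Table 5 grades are unrecoverable. The documents do not support that for the systemic reactions, for the reasons in step 4 of the working.

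On Grade 4, the ruler may be a lay rendering of Table 5. A claim that it over-grades depends on assuming a blister or ulcer without necrosis, so only the wording difference is reported.

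The activity-based intensity definitions in Protocol 13.1.2 might be thought to fill the two gaps in Table 5. They are written for adverse events, and that section brings in solicited reactions as adverse events when they last beyond Day 7. Nothing says that they supplement Table 5.

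On the contact instruction, subjects are also told to call about any reaction that worries them. For the seven systemic reactions the diary grade is equal or higher wherever both scales give a grade, so the diary key would not suppress contact there.

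Finally, both appendices are samples, and the issued versions and study manuals are not available here. That limits what can be said about the data, but not about the mismatch inside the protocol.

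**Conclusion.** The point holds as a minor internal inconsistency. For 8 of 12 solicited reactions the appended tools define Grades 2 and 3 differently from the prescribed scale, and for five of those eight Table 5 is itself incomplete. If the issued tools match the samples, Tables 14.3.1.3, 14.3.1.6 and 14.3.1.8 can mix scales. The non-zero-grade proportion for swelling and the contact instruction may also be affected.

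The counts are of definitions, not subjects. Without reaction rates by grade, no change in any percentage can be given. Where both scales give a grade, the diary tends to grade the seven systemic reactions higher, and the ruler tends to grade intact-tissue swelling lower.

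A reader might infer a bias between lots or a threat to the consistency conclusion. The documents support neither: all three lots use the same tools, the study is observer-blind, the safety results are descriptive, and the HI endpoint does not use these grades. Confidence is high in the wording mismatch and lower in any effect on the data, which depends on the issued tools and on site practice.

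**What to change.** 1. Reconcile Table 5, Appendix 1 and Appendix 2 to one symptom-specific grade text, including Grade 4 for erythema and swelling. The sponsor should decide the definitions; this review does not presume which is right.
2. In the same step, settle the two combinations that Table 5 leaves ungraded for the five grouped reactions, so that the gap is not copied into the diary.
3. Make sure the solicited pages capture every element the reconciled scale uses, such as medical intervention or activity interference for swelling if these are kept.
4. State in SAP 9.1.1 that the tabulated grade is the staff-reviewed grade on that scale.

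Timing matters. The synopsis plans the last blood sample for November 2017, and the SAP is dated 24 January 2018. If collection is already complete, items 1 to 3 help only reuse of the materials. For this trial, the SAP and the table footnotes should then name the scale that the recorded grades actually follow.

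Cost: text alignment, ethics notification of the revised subject material, and one SAP sentence. No extra visits, samples or staff are needed.

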10.3.1.2 Adverse Events

All AEs occurring within 21 days after vaccination will be recorded in the source documents or MA and reported in the “Adverse Event” form in the subject’s eCRF, irrespective of intensity or whether or not they are considered to be vaccination-related.

The intensity of AEs will be graded as: mild (1), moderate (2), severe (3) or potentially life threatening (4), according to the FDA Guidance for Industry ([FDA, 2007](#)). Their causal relationship with the study vaccine will be assessed by the Investigator (definitely not related, probably not related, possibly related, probably related or definitely related); see Section [13.1.9](#) for a definition of these causal relationships.

10.3.1.3 Vital Signs

Vital signs measurements (resting BP, HR, and OT) will be performed as part of screening procedures (prior to eligibility assessment on Day 0) and after the post-vaccination surveillance period.

Oral temperature should be collected in degrees Celsius using a digital thermometer. The OT measurement should not be collected immediately following consumption of a hot or cold beverage or after smoking.

Blood pressure will be taken after the subject has been in a seated position as per the site's standard procedure. The BP measurement should be taken by cuff (manual or automated are both acceptable). Both BP and HR may be repeated once if judged necessary. All measurements (including any repeats) will be recorded in the source documents.

